5. ANALYSIS POPULATIONS

Agreement and authorization of subjects included/ excluded from each analysis population will be conducted prior to the unblinding of the study.

5.1. ALL SUBJECTS ENROLLED POPULATION [ENR]

The all subjects enrolled (ENR) population will contain all subjects who signed an informed consent form.

5.2. Intent-to-Treat Analysis Population [ITT]

The intent-to-treat (ITT) analysis population will contain all subjects in the ENR population who were randomized and subjects will be classified according to randomized treatment.

Author:

Version Number: 3.0

Version Date: 06NOV2019

Template No.: CS_TP_BS016 Revision 5 Reference: CS_WI_BS005

5.3. FULL ANALYSIS SET POPULATION [FAS]

The full analysis set (FAS) analysis population will contain all subjects in the ITT population who have not met any of the following criteria:

- 1. Subjects who did not receive any study drug
- 2. Subjects given wrong drug
- 3. Subjects mis-randomized

5.4. PER PROTOCOL ANALYSIS POPULATION [PP]

The per-protocol (PP) analysis population will contain all subjects in the ITT analysis set who did not experience any reason for exclusion. It will be used for sensitivity analysis of the primary efficacy parameter.

Potential reasons for exclusion include:

- Entering study even though subject did not satisfy the inclusion/exclusion criteria
 - Inclusion/exclusion criteria violations will be as reported on the eCRF. IQVIA Biostatistics will not perform programmed checks of inclusion/exclusion criteria.
- Developing withdrawal criteria during the study and not withdrawing
- Receiving wrong treatment or incorrect dose
- Receiving a prohibited concomitant treatment (protocol sections 5.8.1/5.8.2) which may affect the efficacy of study drug
- Out of window Week 12 study visit/EGD, as defined in section 4.1.2 of the protocol.
- Non-compliance to study drug prior to the Week 12 EGD in the opinion of the investigator.
 - At each study visit the investigator or designee are to report non-compliance to study drug.
 Noncompliance is defined (section 5.10 of the protocol) as taking less than 80% or more than 120% of study drug during any evaluation period (visit to visit).

Protocol deviations will be reviewed by the Sponsor and IQVIA monthly. Decisions on whether deviations are to be considered major or minor will be documented at these meetings. Prior to the interim analysis, a list of major deviations will be provided, and decisions on subjects to be excluded from the PP analysis set will be finalized at an

Document:

Author:

Version Number: 3.0

Version Date: 06NOV2019

Template No.: CS_TP_BS016 Revision 5 Reference: CS_WI_BS005

Page 18 of 70

STATE OF THE PARTY OF THE PARTY

analysis set review meeting and signed off by a representative of the Sponsor.

5.5. SAFETY ANALYSIS POPULATION [SAF]

The safety analysis set (SAF) will contain all subjects who receive at least one dose of study drug and subjects will be classified according to treatment received.

If there is any doubt whether a subject was treated or not, they will be assumed treated for the purposes of analysis.

See section 17 for the handling of safety data for Week 12 histological non-responders who switch to single-blind (to subject) APT-1011 3 mg BID at the end of Part 1 of the study.

5.6. SPARSE PK SUBGROUP

The Sparse PK Subgroup includes all subjects who have ≥1 quantifiable PK sample collected for sparse PK evaluations.

As stated in section 4.3 analyses relating to PK parameters will not be performed by IQVIA Biostatistics and do not form part of this SAP.

6. GENERAL CONSIDERATIONS

6.1. REFERENCE START DATE AND STUDY DAY

Study Day will be calculated from the reference start date, and will be used to show start/ stop day of assessments and events.

Reference start date is defined as the day of the first dose of study drug, (Day 1 is the day of the first dose of study drug), and Study Day will appear in every listing where an assessment date or event date appears. If first dose of study drug is missing, night of randomization will be assumed as Day 1.

For safety analyses of Part 2 of the study, histological non-responders at Week 12 who receive single-blind (to subject) APT-1011 3.0 mg BID during Part 2) will have an additional Study Day for Part 2 based on a reference start date which is day the first dose of study drug in Part 2 (i.e. Week 12 visit + 1 day).

Author:

Version Number: 3.0

Version Date: 06NOV2019

Template No.: CS_TP_BS016 Revision 5 Reference: CS_WI_BS005

Effective Date: 01Apr2018

Page 19 of 70

• If the date of the event is on or after the reference date then:

Study Day = (date of event - reference date) + 1.

• If the date of the event is prior to the reference date then:

Study Day = (date of event - reference date).

In the situation where the event date is partial or missing, Study Day and any corresponding durations will appear partial or missing in the listings.

6.2. BASELINE

Unless otherwise specified, baseline is defined as the last non-missing measurement taken prior to reference start date (including unscheduled assessments). In the case where the last non-missing measurement and the reference start date coincide, that measurement will be considered pre-baseline, but Adverse Events (AEs) and medications commencing on the reference start date will be considered post-baseline.

If any subjects are randomized but do not take study drug, their baseline as defined above will be defined relative to the date of randomization.

Note that for data other than adverse events (see section 17.1) baseline is always relative to the first dose of study drug in Part 1.

6.3. DERIVED TIMEPOINTS

There will be no derived timepoints in this study. EOT visits will be recorded separately and will not be re-mapped.

6.4. RETESTS, UNSCHEDULED VISITS AND EARLY TERMINATION DATA

In general, for by-visit summaries, data recorded at the nominal visit will be presented. Unscheduled measurements will not be included in by-visit summaries, but will contribute to any summaries of clinically significant or markedly abnormal safety data 'at any time post-baseline'.

In the case of a retest (same visit number assigned), the earliest available measurement for that visit will be used for

Author:

Version Number: 3.0

Version Date: 06NOV2019

Template No.: CS_TP_BS016 Revision 5 Reference: CS_WI_BS005

Page 20 of 70

by-visit summaries.

Listings will include scheduled, unscheduled, retest and EOT visit data.

6.5. WINDOWING CONVENTIONS

No windowing or mapping of visits will be conducted. Visits will be included as they are recorded by the site, regardless of study day.

6.6. STATISTICAL TESTS

The default significant level will be 5%; confidence intervals will be 90% and all tests will be one-sided.

6.7. COMMON CALCULATIONS

For quantitative measurements, change from baseline will be calculated as:

Test Value at Visit X – Baseline Value

For certain parameters percentage change from baseline will be calculated as

• 100 x (Test Value at Visit X – Baseline Value)/Baseline Value

6.8. SOFTWARE VERSION

All analyses will be conducted using SAS version 9.4 or higher.

6.9. DATA SOURCES

All data will be retrieved from the eCRF with the following exceptions:

- Number of dysphagia episodes, PGIS, PGIC and Global EoE will be retrieved from the diary
- EoE histological response and EGD will be received from Inform Diagnostics
- Laboratory data will be received from Q2

Author:

Version Number: 3.0

Version Date: 06NOV2019

Template No.: CS_TP_BS016 Revision 5 Reference: CS_WI_BS005

Effective Date: 01Apr2018

Randomization data will be received from Cenduit (after unblinding)

7. STATISTICAL CONSIDERATIONS

7.1. ADJUSTMENTS FOR COVARIATES AND FACTORS TO BE INCLUDED IN ANALYSES

The following covariates and factors are used in the analyses. For details of their inclusion in the models, see the specific analysis section.

- History of or current presence of esophageal stricture (yes/no)
- Prior positive steroid response to any corticosteroid treatment previously received to treat EoE (yes/no)
- Geographic region (North America/Western Europe see section 7.2)
- History of asthma/allergy
- EREFs score
- PPI status

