#### **Eosinophilic Esophagitis Histology**

A central pathologist will evaluate all esophageal biopsies and count the peak number of eosinophils/HPF. Forms to be used for the histology portion of analysis are found in the Central Pathology Laboratory Operations Manual. This number will also be captured in the clinical database.

The pathologist will notify the IWRS vendor of subject eligibility (at baseline), or responder status (at other time points from histology perspective; see also Section 5.7). From a histological perspective, the eligibility requirements are described in Inclusion Criterion # 7 (have evidence of EoE, as defined by  $\geq$ 15 PEAK eosinophils/HPF) in Section 4.2.1 and the responder definition is described in Section 4.1.1.

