## 8.1.1 Expected Number of Subjects by Part

The following assumptions were used:

- The 1:1:1:1 (1.5 mg HS: 1.5 mg BID: 3 mg HS, 3 mg BID: placebo) randomization ratios will remain constant throughout the study.
- Based on these randomization ratios, approximately 80% of all subjects in Part 1 will be treated with an APT-1011 dosing regimen and approximately 20% of all subjects in Part 1 will be treated with placebo.
- Based upon the PR-021 study, which had slightly different histologic response criteria, it is expected that approximately 60% of patients on active treatment are expected to be a histologic responder compared to 10% on placebo. The lowest dose may be less effective.
  - Assuming a 60% histologic response rate for the 3 highest active doses of 1.5 mg BID, 3 mg HS, 3 mg BID, a 20% response rate for 1.5 mg HS, and a 10% response rate for placebo, it is expected that overall approximately 50% of active treatment will be responders at Week 12 (40 out of 80).
  - o It is expected that at Week 26 an additional 20% will drop out who were previously responders and of the PART 1 non-responders that 40% will still be non-responders.
  - After Week 26, of the remaining subjects, it is expected that approximately 20% will dropout before Week 52.

Given these assumptions, it is expected that approximately 42 patients will be responders and complete Week 26, and about 34 of those responders will complete Week 52.

The power for testing each active dose versus placebo given a histologic response rate of 60% active treatment and 10% placebo for the primary endpoint (Part 1) is equal to 97.5% (one-sided Type I error = 0.05). Additionally, the power for achieving statistical significance for all 3 of the highest active doses of 1.5 mg BID, 3 mg HS, 3 mg BID via the gatekeeping hypothesis testing approach assuming independence is approximately 0.93.

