10. DEMOGRAPHIC AND OTHER BASELINE CHARACTERISTICS

Demographic data and other baseline characteristics will be presented for each of ENR set, the ITT analysis set, the FAS analysis set, and the SAF.

No statistical testing will be carried out for demographic or other baseline characteristics.

The following demographic and other baseline characteristics will be reported for this study:

- Sex (Male/Female)
- Race (White, Black or African American, Asian, American Indian or Alaska Native, Native Hawaiian or other Pacific Islander, Other)
- Ethnicity (Hispanic or Latino/Not Hispanic or Latino)
- Age (years) calculated relative to date of informed consent
- Geographic region (North America/Western Europe)
- Weight (kg)

Author:

Version Number: 3.0

Version Date: 06NOV2019

Template No.: CS_TP_BS016 Revision 5 Reference: CS_WI_BS005

Effective Date: 01Apr2018

Page 25 of 70

- Height (cm)
- Body mass index (BMI) (kg/m²)
- Smoking status (Never/Former/Current)
- Global EoE symptom score
- History of esophageal stricture(s) (Yes/No)
- Current esophageal stricture(s) based on the study esophagogastroduodenoscopy (EGD) (Yes/No)
- History of a positive steroid response to EoE treatment (Yes/No)
- PPI status (Continuing Yes/No)

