16.1.2. MISSING DATA METHODS FOR PRIMARY EFFICACY VARIABLE

For the primary analysis of the primary efficacy variable, any subject who does not meet the definition of responder, will be classified as a non-responder. This includes subjects who withdraw from the study prior to the week 12 histological assessment.

The primary analysis of the primary efficacy variable is via a stratified Cochran-Mantel-Haenzel (CMH) test, as described in section 16.1.3.

A sensitivity analysis, described in section 16.1.4 will be performed with missing response data imputed using multiple imputation, assuming the data are missing at random.

Multiple imputation will be used to provide estimates of the common odds ratio, its 90% confidence interval and associated 1-sided p-value.

The dataset containing subject, dosing group, week 12 histologic response, the two randomization strata, history of asthma/allergy, baseline EREF score, and PPI status will be used as the basis for multiple imputations. Histologic response will be set to missing for those subjects who did not have a Week 12 result for peak eosinophils/HPF (and for whom response status was set to non-responder in the primary efficacy analysis).

The methodology which follows in this section are taken from a 2013 paper by Ratitch, Lipkovich and O'Kelly. The imputation method will be based on logistic regression using the MONOTONE statement of PROC MI in SAS

Author:

Version Number: 3.0

Version Date: 06NOV2019

Template No.: CS_TP_BS016 Revision 5 Reference: CS_WI_BS005

Page 30 of 70

as shown below.

The option NIMPUTE in the PROC MI statement will be used to specify the number of imputed datasets to be generated. The output dataset will contain 500 copies of the original dataset, with the observed values being the same across all datasets, and with imputed values varying from one dataset to another. These multiple copies will be identified by a new variable, Imputation, added to the output dataset by PROC MI.

The SAS Code to perform the imputations is provided below. The SEED and NIMPUTE value are explicitly stated here to enable results to be replicated and quality assured.

```
PROC MI DATA=datain OUT=datain mi SEED=1201913 NIMPUTE=500;
VAR dosegrp strata1 strata2 asthma EREF PPI response;
CLASS dosegrp strata1 strata2 response;
MONOTONE LOGISTIC;
RUN;
```

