16.1.5. SECONDARY ANALYSES OF THE PRIMARY EFFICACY VARIABLE

- Bayesian hierarchical modeling will be used for both the primary efficacy endpoint and reduction in number of dysphagia episodes, in which dose-response modeling is used to estimate the difference between each APT-1011 dosing group and placebo.
- Terms in the Bayesian models will include dose (3 mg, 1.5 mg, or 0 mg), frequency (BID or HS, with placebo subjects included as BID), and the two randomization strata. Posterior estimates for each of the model coefficients will be generated through Monte Carlo Markov Chains (MCMC) using the Metropolis random walk sampling algorithm. Initially the first 2000 simulations will be discarded for burn-in and the subsequent 10000 samples retained for posterior estimation. Trace iteration plots and autocorrelation plots of the simulated samples will be examined with standard diagnostic tests to establish convergence of the posterior samples. If sufficient convergence of all parameters has not been achieved the burn-in period and number of simulations will be revised and different sampling algorithms will be considered.
- The proportion of responders at each dose level and frequency will be estimated from the respective posterior distributions. Estimates of the difference in the proportion of responders between each active dose level and placebo will be calculated using the distributions of the differences between posterior estimates along with 90% credible intervals of these estimates. The probability that the difference is greater than 0 will also be displayed. In addition the posterior distributions of each difference estimate will be produced along with the estimated dose-response curve. Estimates of the dosing frequency and stratification effects will also be displayed for all dose groups.
- A logistic regression model using both dose and frequency and dose-frequency interaction will be used to analyze the primary efficacy variable. Separate terms will be included in the model for dose (3 mg, 1.5 mg or 0 mg (placebo) frequency (BID or HS, with placebo subjects included as BID) and dose-frequency interaction.

Two models will be used. One containing just dose, frequency and dose-frequency interaction. The other will

Author:

Version Number: 3.0

Version Date: 06NOV2019

Template No.: CS TP BS016 Revision 5

Reference: CS WI BS005

Effective Date: 01Apr2018

Page 36 of 70

additionally contain randomization strata.

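### In the visible plan the peak eosinophil count is analysed only through cut-offs and its baseline value enters no model; the cost falls on dose-response and the lowest dose, not on the primary test

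*SAP*

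**What the plan says.** The count exists as a number. Under Eosinophilic Esophagitis Histology the protocol states: "A central pathologist will evaluate all esophageal biopsies and count the peak number of eosinophils/HPF". The same paragraph says that the number goes into the clinical database. Inclusion criterion 7 requires at least 15/HPF on the central reading and sets no upper limit, so every eligible randomized subject has a baseline value.

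The visible analyses use the post-baseline count only through thresholds: ≤6 for the primary endpoint (SAP 16.1.1) and its complement, non-response (16.2.1.11), and <1 and <15 as secondary endpoints (16.2.1.3).

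The baseline count is absent from each place where it could have been used:

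- SAP 7.1, which begins "The following covariates and factors are used in the analyses", lists stricture, prior steroid response, region, asthma/allergy, EREFs and PPI status. The sensitivity logistic regression (16.1.4) and the secondary ANCOVAs (16.2.3.4) draw on that list.
- SAP 16.1.2 builds the imputation on subject, dosing group, response and these variables: "the two randomization strata, history of asthma/allergy, baseline EREF score, and PPI status will be used as the basis for multiple imputations".
- SAP 16.1.5: "Terms in the Bayesian models will include dose", frequency and the two strata. The dose-frequency logistic models hold dose, frequency and their interaction, with the strata added in the second.
- SAP 10, under "The following demographic and other baseline characteristics will be reported for this study", includes the Global EoE symptom score, strictures, steroid response and PPI status.

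**The concern.** Defining the dose-response and selecting a Phase 3 dose are secondary objectives (protocol 3.2). Both depend on comparing active doses with each other and on placing the lowest dose, with 20 subjects per arm. Reducing a count to yes/no gives up power, and it matters most where power is already low.

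The plan also treats its outcomes unevenly. EREFs, the Global EoE score and the EEsAI each get a change-from-baseline ANCOVA. Histology, the primary domain, has a numeric measure but no analysis on its own scale. Baseline EREFs helps to impute histologic response, while the baseline value of the histologic measure itself does not.

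**Working it through.** **Inputs.** Protocol 8.1 and 8.1.1 give 20 per arm, "one-sided Type I error = 0.05", and the power of each active dose v placebo: "given a histologic response rate of 60% active treatment and 10% placebo for the primary endpoint (Part 1) is equal to 97.5" per cent. For the lowest dose they assume "a 20% response rate for 1.5 mg HS, and a 10% response rate for placebo". The rates 60% v 80% are an assumption made here. So are normality of the log count, its SD (1.3, used only in the simulation), the baseline distribution (median about 45, truncated at 15) and any correlation between baseline and Week 12.

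**1. The plan's own figure.** For two proportions with pooled null variance, power = Φ[(p1 − p0 − 1.645·s0)/s1], where s0 = √(2·p̄(1 − p̄)/20) and s1 = √((p1(1 − p1) + p0(1 − p0))/20).

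For 60% v 10%: s0 = 0.1508, s1 = 0.1285, and (0.5 − 0.2481)/0.1285 = 1.961, so power is 97.5%. Cubed, this gives 0.927, the protocol's approximate 0.93 for three doses. Both figures reproduce.

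**2. Dichotomy against log count, no baseline term.** If log counts are normal with equal SD, response rates p1 and p0 imply means δ = z(p1) − z(p0) SDs apart. A t-test with 20 per arm then has non-centrality δ/√(2/20) = δ/0.316 on 38 df.

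| Rates | Dichotomy, formula | Dichotomy, simulated | δ | δ/0.316 | t-test, formula | log(count + 1), simulated |
|---|---|---|---|---|---|---|
| 10 v 20% | 22% | 23% | 0.440 | 1.39 | 39% | 39% |
| 20 v 60% | 85% | 84% | 1.095 | 3.46 | 96% | 96% |
| 60 v 80% (assumed) | 39% | 41% | 0.588 | 1.86 | 57% | 56% |

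The simulations used 20,000 trials with whole-number counts, including zeros. At 60 v 80%, where zeros are most common of the three, a rank test gave 54%.

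**3. What the baseline covariate adds.** Adjusting the dichotomy at 60% v 10% moved simulated power from 97.5 to 97.7% at correlation 0.2, from 97.8 to 98.1% at 0.3, and from 97.7 to 98.8% at 0.5. That is 0.2 to 1.1 points. Adding baseline to the log-count analysis at correlation 0.5 moved power from about 39 to 46% (10 v 20%), from 96 to 99% (20 v 60%) and from 56 to 65% (60 v 80%). At correlation 0 there was no gain.

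**4. Information kept by a cut-off.** Under the same normal model the fraction is φ(z)²/[p(1 − p)] at the mid-point responder rate p: 58% at 70% (60 v 80%), 62% at 40% (20 v 60%) and 43% at 15% (10 v 20%).

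**5. Chance imbalance at baseline.** The SD of a difference in arm means is √(2/20) = 0.316 SD. The chance that one dose differs from placebo by more than 0.5 SD is 2[1 − Φ(0.5/0.316)] = 11.4%. Simulated over four doses sharing one placebo arm, the chance of at least one such difference is 32%.

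**The case against.** The strongest objection is that the primary analysis does not need this. It has 97.5% power on the planned assumptions, a CMH test cannot take a continuous covariate without banding, and logistic adjustment gives a conditional odds ratio whose standard error on the log scale does not shrink. All of that stands, and it is why the CMH test should not change.

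A reader might infer that the primary endpoint loses precision, that baseline imbalance is likely, or that the cut-off discards most of the information. The documents and the arithmetic do not support these readings. Primary power moves by about a point or less at correlations up to 0.5. An imbalance above 0.5 SD has an 11.4% chance per dose, and nothing in the documents shows that baseline count is prognostic. The cut-off keeps 58% to 62% of the information for the between-dose contrasts; only at 10 v 20% does it keep less than half. Most of the gain comes from analysing the count, not from the covariate.

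The protocol also assumes one common rate of 60% for the three higher doses, so on its own assumptions they do not differ, and its 20 v 60% contrast already has about 84% power. That is fair. It leaves the lowest dose against placebo, and any departure from the common rate, which a dose-ranging trial is meant to detect.

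Finally, the exploratory endpoint text (protocol 6.2.8.3, SAP 16.3) is not visible and the table templates are not supplied. SAP Appendix 1 asks for CRF variables to be listed, and SAP 3.3 defers exposure-response work to a possible separate plan. Statements that the count is used only through cut-offs and in no model therefore hold for the visible text. None of the excluded exploratory outputs named in SAP 3.3 is described as an analysis of the count on its own scale.

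**Conclusion.** The point holds for dose-response and the lowest dose, within the visible text. Analysing the count instead of the ≤6 dichotomy would raise power by about 16 points at 10 v 20%, 12 points at 20 v 60% and 15 points at an assumed 60 v 80%. These figures rest on normal log counts, 20 evaluable subjects per arm with no dropout, and no stratification. Any further gain from baseline adjustment depends on a correlation that the documents do not give.

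The primary conclusion is not at risk. Nor would the fix raise the power of the formal test of 1.5 mg HS, which stays a CMH test; it adds supportive evidence beside it.

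Timing limits what can be claimed. Protocol 2.5, in the text dated 16 Jul 2019, reports that the Week 12 endpoint was met at all doses and that a dose has been chosen. SAP v3.0 is dated 06 Nov 2019. A reader might think the gain comes free because the data are already held, but any addition now is post hoc and must be labelled so.

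**What to change.** Keep the stratified CMH test as the primary analysis, unchanged. Then:

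- List baseline peak eosinophils/HPF by dosing group in SAP 10.
- Add log(baseline peak count) as a fixed covariate, exempt from stepwise selection, to the supportive logistic regression, the imputation model and the Bayesian model of histologic response.
- Add one supportive dose-response analysis: ANCOVA of log(Week 12 peak count + 1) on arm, the two randomization strata and log baseline count.
- Because of zeros and missing counts, accompany it with a rank-based check in which subjects without a Week 12 count take the worst rank, in line with the non-responder rule in SAP 16.1.2.
- Label all of these supportive and post hoc.

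The cost is SAP wording and a little more programming and reporting. No new data are needed. The downside is that the results can support, but not confirm, a dose-response conclusion.
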